6.2.2 Safety

The analysis visit windows for safety endpoints, including laboratory assessments, are defined as follows:

Table 6-3 Safety Analysis Visit Definitions

Analysis Phase	Analysis Visit (Derived)	Scheduled Study Visit (eCRF)	Window
Part 1 & Part 2			
Treatment	Month 1	Day 30	Treatment Day [2, 60]
	Month 3	Day 90	Treatment Day [61, 135]
	Month 6	Day 180	Treatment Day [136, 225]
	Month 9	Day 270	Treatment Day [226, 315]
	Month 12	Day 360	Treatment Day [316, 405]
	Month X (every 6 months)	Day X*30	Treatment Day [X*30-44, X*30+45], where X=18, 24, 30, ..., 84, 90, 96
	30-Day FU	Day X*30 +30	Treatment Day [X*30-44, X*30+45] +30, where X=18, 24, 30, ..., 84, 90, 96
	End of study	Final or termination visit	Last non-missing assessment after treatment start date in Part Y / between Treatment Day 2 in Part Y and Off-treatment Day 30, inclusive, where Y=1,2.

The following general conventions for repeated or unscheduled assessments will apply unless otherwise specified:

- For scheduled and unscheduled assessments, if more than one assessment is measured within the same visit window, then the record with the latest visit date (from baseline) will be used for that visit window.
- All assessments will be included in respective listings.

For plasma and serum samples for storage, samples at visits beyond baseline (Visit 2) can be used for checking polymorphisms, genotype status, and pharmacogenetic biobanking.

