6.1.1 Analysis Days

Treatment days are defined as follows:

Table 6-1 Analysis Day Definitions

Term	Description
Treatment Day	Relative to treatment start date If analysis date \geq treatment start date: 
• Day = analysis date – treatment start date + 1
○ Day 1 = treatment start date If analysis date < treatment start date: 
• Day = analysis date – treatment start date
○ Day -1 = day before treatment start date○ There is no Day 0

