6.2 Analysis Visit Windows

6.2.1 Efficacy

The analysis visit windows for efficacy endpoints, including liver biopsy, are defined as follows:

Table 6-2 Efficacy Analysis Visit Definitions

Analysis Phase	Analysis Visit (Derived)	Study Visit (eCRF)	Window
Part 1 & Part 2			
Pretreatment	Baseline	Day 1	Treatment Day ≤ 1 , pre-randomization in Part Y
Treatment	Month 12	Day 360	Treatment Day [316, 405], post-randomization in Part 2 Note: For the primary efficacy analysis in Part 1 using the mITT analysis set, any available liver biopsy after randomization will be used for the Month 12 biopsy, no matter when it was obtained relative to the first dose of study drug. Subjects with multiple liver biopsies will have the evaluable biopsy closest to the Month 12 visit included in the analysis.
	Month 60	Day 1800	Treatment Day [1756, 1845], post-dose in Part 2
	End of study	Final or termination visit	Last non-missing assessment during the Treatment Period in Part Y / between Treatment Day 1 in Part Y, post-dose, and Off-treatment Day 1, inclusive, where Y=1, 2.

The following general conventions for repeated or unscheduled assessments will apply unless otherwise specified:

- For scheduled and unscheduled assessments, if more than one assessment is measured within the same visit window, then the record with the latest visit date (from baseline) will be used for that visit window.
- All assessments will be included in respective listings.

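### The SAP counts its 30-Day Follow-up window from first dose, so it takes in six-monthly visit days of subjects still on drug and misses the Follow-up visit of anyone who stops before Day 496

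*SAP*

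**What the plan says.** SAP Section 4.1.1 (Overall Design) has subjects return for a Follow-up visit, numbered Visit 98, 30 days after their final dose. The protocol (Section 7.1) says the same.

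SAP Table 6-3 assigns safety assessments to derived analysis visits. The six-monthly rows read "Treatment Day [X*30-44, X*30+45], where X=18, 24, 30, ..., 84, 90, 96". The 30-Day FU row reads "Treatment Day [X*30-44, X*30+45] +30", for the same values of X. Table 6-1 defines Treatment Day from the treatment start date: "Day = analysis date – treatment start date + 1". The FU row mentions neither the treatment end date nor any off-treatment condition. The End of study row of the same table does have one: "between Treatment Day 2 in Part Y and Off-treatment Day 30, inclusive".

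When several assessments share a window, "then the record with the latest visit date (from baseline) will be used for that visit window". There is no rule for one assessment that falls in two windows.

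Table 5-19 asks for laboratory values by analysis visit, including a 30-Day Follow-up in Part 1. Table 5-21 does the same for vital signs. Both carry a footnote saying that they are based on nominal visits in the schedule of assessments.

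**The concern.** The visit is defined by the last dose, its analysis window by the first dose. The two agree only for certain stopping days.

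Two errors follow if Table 6-3 is programmed as written. Laboratory values and vital signs from subjects still taking study drug can qualify as 30-Day Follow-up. True post-treatment values from subjects who stop early can be labelled as an on-treatment month or get no by-visit label at all. At stake is whether the by-visit safety tables keep on-drug and post-drug values apart, and whether two programmers working from the same SAP would produce the same table.

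**Working it through.** **Inputs.** The window formulas and the latest-record rule come from SAP Table 6-3 and its notes, the day count from Table 6-1, and the timing of the visit from SAP Section 4.1.1.

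**Check of the Month X formula, [30X - 44, 30X + 45].**
- X = 12: 360 - 44 = 316 and 360 + 45 = 405, the Month 12 window written out in Table 6-3.
- X = 60: 1800 - 44 = 1756 and 1800 + 45 = 1845, the Month 60 window in Table 6-2 ("Treatment Day [1756, 1845], post-dose in Part 2").

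The formula reproduces the SAP's own figures.

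**Follow-up window.** Adding 30 to both bounds gives [30X - 14, 30X + 75].

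**Overlap.** The two windows share days 30X - 14 to 30X + 45, which is 45 + 14 + 1 = 60 of the 90 days in the Month X window. The scheduled day 30X always lies in the shared stretch.

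| X | Scheduled day | Month X window | FU window | Shared days |
|---|---|---|---|---|
| 18 | 540 | 496-585 | 526-615 | 60 |
| 24 | 720 | 676-765 | 706-795 | 60 |
| 60 | 1800 | 1756-1845 | 1786-1875 | 60 |
| 96 | 2880 | 2836-2925 | 2866-2955 | 60 |

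There are (96 - 18)/6 + 1 = 14 such visits, and all 14 scheduled days fall in both windows. The same holds with calendar months of 30.4375 days. It also holds if the 30 days are added only to the upper bound, because 30X lies between 30X - 44 and 30X + 75.

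**Where the true Follow-up visit lands.** With a last dose on Treatment Day s, an on-time Follow-up is on Day s + 30. It is in an FU window when 30X - 14 <= s + 30 <= 30X + 75, that is, when 30X - 44 <= s <= 30X + 45. The last dose itself must therefore fall in a Month X window with X of at least 18. The first such day is 496.

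| Last dose (Day) | Follow-up (Day) | Windows it falls in |
|---|---|---|
| 180 | 210 | Month 6 |
| 360 | 390 | Month 12 |
| 450 | 480 | none |
| 495 | 525 | Month 18 only |
| 496 | 526 | Month 18 and FU |
| 585 | 615 | FU only |
| 586 to 645 | 616 to 675 | none |
| 646 | 676 | Month 24 only |

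Month X windows are 90 days wide and recur every 180 days, so about half of later stopping days miss too. Of the 2341 possible last-dose days from 540 to 2880, 1171 (50%) put the Follow-up in an FU window.

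**Effect of the latest-record rule.** A subject has the Month 6 visit on Day 180, stops that day and attends Follow-up on Day 210. Both days lie in the Month 6 window (136-225). The later record is used, so the off-drug value replaces the on-drug value at Month 6.

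**The case against.** The strongest reply is that follow-up may never be tabulated from Table 6-3. The nominal-visit footnote closes timing lists that include Follow-up in Tables 5-19 and 5-21. The same marker appears in Table 5-22, whose list has no Early Discontinuation visit, so it is not specific to that visit. Follow-up also has its own number, Visit 98, and can be identified without a window. This is a reasonable reading and would limit the harm. It does not settle the matter: Tables 5-19 and 5-21 also say they summarise by analysis visit, and Table 6-3 still derives a 30-Day FU visit. If nominal visits govern, that row is redundant. The schedule of assessments that the footnote cites is not visible in the public copy, so it cannot decide the question.

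A second reply is that X means the month in which the subject stopped. The row does not say so, and early stoppers would still have no window. A stop on Day 540 would put Follow-up on Day 570, in both the Month 18 and FU windows, where it would displace the Day 540 value at Month 18.

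A third reply concerns scope, and it stands. A reader might infer that the liver-safety signal is compromised. The documents do not support that:
- Table 5-20 counts liver elevations up to 30 days after treatment end.
- Toxicity grades pool all post-baseline values.
- The End of study row has its own off-treatment limit.
- Suspected drug-induced liver injury is adjudicated and reviewed by the DSMB.
- All assessments are listed.
- The SAP plans no analysis of recovery after stopping.

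**Conclusion.** The point holds as a defect in one derived-visit row. All 14 six-monthly visit days from Month 18 to Month 96 fall in two windows. No subject whose last dose is before Day 496 has an on-time Follow-up in an FU window, although a Part 1 follow-up summary is planned. About half of later stopping days fail as well. The effect is confined to descriptive by-visit summaries of laboratory values and vital signs; no hypothesis test and no efficacy analysis is involved.

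Two broader readings are tempting and wrong. One is that every on-schedule visit from Month 18 is double-labelled. Part 2 visits are three-monthly, and the intermediate ones fall in neither window: Month 21 is Day 630, after the X=18 FU window ends (Day 615) and before Month 24 opens (Day 676). The other is that everyone stopping before Month 18 (Day 540) lacks a window. Stops on Days 496-539 give Follow-up on Days 526-569, inside the X=18 FU window, though also inside Month 18. The cutoff is Day 496.

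The result assumes that Table 6-3 is applied literally and that Follow-up takes place exactly 30 days after the last dose. If follow-up is tabulated by nominal visit, the follow-up summary itself is sound and what remains is a conflict of wording to resolve, together with the question of whether Follow-up records also enter the Month X windows.

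**What to change.** Choose one of two routes:
- Anchor the 30-Day FU row to the treatment end date, with target last dose + 30 days and a width chosen by the sponsor. The SAP gives no width. Any half-width from 0 to 29 days captures an on-time Follow-up for every stopping day and excludes every visit of a subject still on drug.
- State that Follow-up is tabulated by nominal visit (Visit 98), delete the derived row, and align the wording of Tables 5-19 and 5-21.

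Under either route, define Off-treatment Day in Table 6-1, which at present defines only Treatment Day although Tables 6-2 and 6-3 use the other term. Add a precedence rule that a record assigned to Follow-up is not also used in a Month X window.

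Do not cut the Month X windows at the last dose. Subjects who stop drug are encouraged to continue their visits (SAP Section 4.1.1), and a cut would leave those assessments without a window. Flag such records as off-drug instead.

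The cost is one corrected or deleted row, one definition and one sentence on precedence, before database lock. One side effect under the first route: a scheduled visit that happens to fall about 30 days after stopping would count as Follow-up only and drop out of its Month X summary.

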#### *11.3.2.2. Clinically Significant Laboratory Abnormalities*

Any laboratory test showing abnormal results (including those recorded as AEs) that are believed to be possibly/probably related to study drug treatment will be repeated weekly (or as often as deemed prudent by the investigator) until the abnormality is resolved (if baseline was within normal range), returns to Baseline range (if baseline was abnormal), or is otherwise explained. Whenever possible, the etiology of the abnormal findings will be documented on the eCRF. See Section 11.3.1.1.7 for a definition of clinically significant laboratory abnormality.

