**For detailed management of subjects with ALT, AST, ALP, or bilirubin elevations, see Section 11.3.6.4.**

[figure not shown]
For Grade 4 laboratory abnormalities, a confirmatory measurement should be obtained within 48 to 72 hours after the laboratory results become available.

[figure not shown]

[figure not shown]

[figure not shown]

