5.1.1.4.3 Clinical Laboratory Assessments

Clinical laboratory assessments will be summarized by treatment group for the Safety Population as follows:

Table 5-19 Clinical Laboratory Summaries

Type of Endpoint	Description	Timing	Methodology
Laboratory values over time	Summary by laboratory category and parameter in SI units and analysis visit 
 • Parameters specified in Section 6.6.2.2 	Part 1: Screening, Baseline (Day 1), Months 1, 3, 6, 9, 12, and 30-Day Follow-up, Early DC ¹ Part 2 (subjects newly randomized in Part 2): Screening, Baseline, Months 1, 6, 12 Part 2 (all subjects (continuing from Part 1 and newly randomized in Part 2): Every 6 months from Month 18 through Month 96 End of Study Part 1 and Part 2: Follow-up, Early Discontinuation Visit ¹	CFB descriptive statistics
Laboratory abnormalities by toxicity grade	Summary by laboratory category and parameter 
 • Grade 1, Grade 2, Grade 3 and Grade 4 categories based on NCI CTCAE version 4.03 • Parameters specified in Table 6-8 • Include all post-baseline combined for counts of toxicity by grade. Only treatment-emergent laboratory abnormalities should be summarized in laboratory abnormalities by grade – must have a toxicity that is a higher grade than at baseline to be included.	Part 1: Screening, Baseline (Day 1), Months 1, 3, 6, 9, 12, and 30-Day Follow-up, Early DC ¹ Part 2 (subjects newly randomized in Part 2): Screening, Baseline, Months 1, 6, 12 Part 2 (all subjects (continuing from Part 1 and newly randomized in Part 2): Every 6 months from Month 18 through Month 96 End of Study Part 1 and Part 2: Follow-up, Early Discontinuation Visit ¹	Categorical descriptive statistics

¹ Based on nominal visits defined in the schedule of assessments.

5.1.1.4.3.1 Liver Biochemistry

Elevations of ALP, ALT, AST, or bilirubin, or confirmed ALP, ALT, AST, or bilirubin elevations (with or without liver-related clinical symptoms) will be summarized by treatment group for the Safety Population as follows:

Table 5-20 Liver Biochemistry Summaries

Type of Endpoint	Description	Timing	Methodology
ALP, ALT, AST, or bilirubin elevations with or without liver-related clinical symptoms	ALP, ALT, AST, or bilirubin elevations with or without liver-related clinical symptoms (with or without confirmatory measurement), based on protocol Table 11-1	Treatment Period + 30 days after treatment end date	Categorical descriptive statistics

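### SAP 6.2.2 takes the latest record in each safety window, so the by-visit laboratory table can show a recovered retest in place of the abnormal scheduled value

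*SAP*

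**What the plan says.** **Selection rule.** The conventions under SAP Table 6-3 cover scheduled and unscheduled assessments alike: "if more than one assessment is measured within the same visit window, then the record with the latest visit date" supplies the value for the visit. They hold unless otherwise specified. SAP 6.2.2 says that the windows apply to safety endpoints, laboratory assessments included.

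**Where the rule acts.** The first row of SAP Table 5-19 (laboratory values over time) is specified as "Summary by laboratory category and parameter in SI units and analysis visit", with change-from-baseline descriptive statistics. The analysis visit is the derived visit of Table 6-3.

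**Why repeat records exist.** Protocol 11.3.2.2, restated in SAP 6.6.2.1, says that abnormal results believed possibly or probably related to study drug "will be repeated weekly (or as often as deemed prudent by the investigator) until the abnormality is resolved", returns to the baseline range or is otherwise explained. For Grade 3 and Grade 4 laboratory abnormalities (Protocol 11.3.6.2 and 11.3.6.3), "a confirmatory measurement should be obtained within 48 to 72 hours after the laboratory results become available". Protocol 11.3.2.1 also has central INR values above 1.5 repeated.

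**What keeps every value.** The second row of Table 5-19 (toxicity grade) pools all post-baseline values. Table 5-20 counts ALP, ALT, AST and bilirubin elevations, confirmed or not, over treatment plus 30 days. SAP 6.2.2 keeps all assessments in the listings.

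**The concern.** Each rule is reasonable alone, but together they select on the outcome. A normal scheduled value normally stands as the only record in its window. An abnormal one prompts further tests, and the SAP then reports the last of them. Where follow-up runs until the value has recovered, the last record tends to be the recovered one.

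It may also be an off-drug value. Treatment Day is counted from treatment start (SAP 6.1.1). The month windows sit under a phase labelled Treatment, but no cut-off at the end of treatment is written for them, and subjects who stop drug are encouraged to stay in the study.

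At stake is the planned display of time course and mean shift in laboratory values. Liver biochemistry elevations are the protocol's adverse events of special interest. If such elevations were more frequent on CVC than on placebo, more abnormal values would be replaced in the CVC arm, and the by-visit difference would move towards zero.

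**Working it through.** The documents give no figure to reproduce here, so the check is how much room each window leaves for retests.

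**Inputs.** Target days and window limits come from SAP Table 6-3; the weekly interval comes from Protocol 11.3.2.2.

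**Formulas.** Width = end − start + 1. Days left after an on-time visit = end − target day. Weekly retests that fit = days left ÷ 7, rounded down. Longest elevation, counted from the target day, that can be replaced = 7 × retests.

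| Visit (target day) | Window | Width | Days left | Weekly retests | Longest replaced |
|---|---|---|---|---|---|
| Month 1 (30) | 2 to 60 | 59 | 30 | 4 | 28 days |
| Month 3 (90) | 61 to 135 | 75 | 45 | 6 | 42 days |
| Month 6 (180) | 136 to 225 | 90 | 45 | 6 | 42 days |
| Month 9 (270) | 226 to 315 | 90 | 45 | 6 | 42 days |
| Month 12 (360) | 316 to 405 | 90 | 45 | 6 | 42 days |
| Month X (30X), X = 18, 24, ..., 96 | 30X−44 to 30X+45 | 90 | 45 | 6 | 42 days |

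**Example.** A result abnormal on Day 180 and repeated weekly can have retests on Days 187, 194, 201, 208, 215 and 222, all inside the Month 6 window. If it is back to normal on Day 201 and testing stops, the Month 6 value is the Day 201 value. If it is still abnormal on Day 222, the Month 6 value remains abnormal.

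**How often replacement would occur (assumption).** The documents give no durations. Take exponential durations with mean m days and weekly retests, and let L be the longest replaceable elevation. The probability of replacement is 1 − exp(−L/m):

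| Mean duration m | Month 1 (L = 28) | Month 3 on (L = 42) |
|---|---|---|
| 14 days | 86% | 95% |
| 30 days | 61% | 75% |
| 60 days | 37% | 50% |

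**Effect on a between-arm mean (assumption).** Attenuation = (difference in frequency) × (rise) × (fraction replaced). Suppose 3% on CVC and 1% on placebo have a value 190 U/L above their usual level at a visit. The true difference is (0.03 − 0.01) × 190 = 3.8 U/L. With 50%, 75% or 95% replaced, the table loses 1.9, 2.85 or 3.6 U/L of it. With equal frequencies and equal replacement in the two arms, the loss between arms is 0, though each arm's own mean still falls. For context, Protocol 5.3.3 reports suspected-DILI criteria met by 3.3% in each Phase 2b arm (4/121, 2/61, 2/60).

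**The case against.** **The retest rule is narrower than all abnormal values.** This stands. Follow-up to resolution applies only to results believed drug-related, may be weekly or at the investigator's discretion, and may end because the result has been explained. The Grade 3/4 and INR repeats carry no drug-relatedness condition, but they are confirmations and need not show recovery. A reader might infer that every elevation is overwritten; the documents do not support that. Replacement needs a resolved retest inside the same window. Otherwise the last record stays abnormal, or the retest falls in the next window or, from Month 12 on, in one of the 90-day gaps that Table 6-3 leaves uncovered (Days 406 to 495, for example).

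**Liver tests have their own rules.** This stands too. The Grade 3 and 4 sections refer ALT, AST, ALP and bilirubin elevations to Protocol 11.3.6.4, which is not visible in the public text. Weekly retesting of those four tests is therefore an assumption.

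**The nominal-visit footnote may settle the matter.** In Tables 5-19 and 5-21 the marker sits on the Early Discontinuation entries. In Table 5-22 it follows the post-biopsy entry, and there is no Early Discontinuation entry. It could thus be read as covering the whole visit list, which might keep unscheduled retests out. That reading conflicts with the by-analysis-visit wording in the same rows and with Table 6-3. It is an ambiguity to resolve and does not answer the point.

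**The bias can run the other way.** An elevation first found at a later unscheduled visit would replace a normal scheduled value. This is possible, but follow-up to resolution makes the opposite direction the systematic one.

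**The liver signal is safe elsewhere.** This stands, and it limits the point. A reader might infer that the plan hides hepatotoxicity. It does not: the toxicity-grade table, Table 5-20, expert DILI adjudication with DSMB review, and the listings all retain the elevations. No safety hypothesis is tested.

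**Conclusion.** As written, the latest-record rule can replace an on-schedule abnormal laboratory value with a later, recovered and possibly off-drug one in the values-over-time row of Table 5-19. By-visit means and changes from baseline can then be biased towards no effect. There is room for this within 28 days of an on-time Month 1 visit and within 42 days from Month 3 on, if retests are weekly.

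The actual size is unknown. It depends on how long elevations last, how often investigators retest, whether frequencies differ between arms, and a liver-specific schedule that cannot be seen. The percentages and U/L figures above only illustrate stated assumptions. The consequence is confined to a descriptive by-visit display. The point is worth correcting because that table is the planned view of time course and mean shift, and because the correction is nearly free.

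**What to change.** In SAP 6.2.2, for by-visit laboratory summaries:

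- Use the scheduled-visit record. If there is none in the window, use the record closest to the target day, with the earlier record on ties.
- Do not let an unscheduled retest replace a scheduled value.
- Keep all records, retests included, for the toxicity-grade table and for Table 5-20.
- State whether the nominal-visit footnote in Tables 5-19, 5-21 and 5-22 applies to every listed visit or only to the entry that carries the marker.

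The SAP already uses a closest-record rule for biopsies at Month 12 (Tables 5-14 and 6-2), so the convention is not new to the document. The change is limited to laboratory data because the follow-up-to-resolution rule covers laboratory tests only.

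The cost is a short SAP edit and a small change to the programmed record selection. It needs no new data and can be made before database lock.
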